6.2 Subgroup analyses

Subgroups analyses will be performed in individual treatment groups, both overall and by arm, will be presented descriptively.

6.3 Analysis of exploratory endpoints

The robustness of the results on the primary and secondary endpoints will be assessed using the exploratory outcomes as presented in the table below.

Table 2: List of exploratory outcomes that are used in the analyses.

Logistic regression with the treatment, and study as factors will be used. Exact logistic regression will be considered if the sample size is too small for a regular logistic regression and/or if some of the cells have no observations. Separate analysis will be performed for biomarker/no biomarker using the ITT population. Statistical analysis Mixed-effects modelling will be performed with treatment, time and patient as factors, and baseline score as covariate. If the assumptions of the Mixed-effects modelling are not met, the data will be analysed GEE methods.	
Mixed-effects modelling will be performed with treatment, time and patient as factors, and baseline score as covariate. If the assumptions of the Mixed-effects modelling are not met, the	
patient as factors, and baseline score as covariate. If the assumptions of the Mixed-effects modelling are not met, the	
Statistical analysis	
requency and percentage of each outcome will be reported by treatment and biomarker using the safety analysis set (SAF).	
Statistical analysis	
Pearson or Spearman (rank) correlation coefficients will be used to assess the correlation between two continuous measures depending on normality.	
T-test or Mann-Whitney test will be used to assess the association	

Association between disease
outcome (binary variables),
treatment group and ultrasound
measure of inflammation
Association between disease
outcome (binary variables),
treatment group and disability
Association between disease outcome
(continuous variables), treatment group
and synovial histology (binary variables)
Association between disease outcome
(continuous variables), treatment group
and synovial histology (continuous
variables)
Association between disease outcome
(continuous variables), treatment group
and Ultrasound measure of inflammation
Association between disease outcome
(continuous variables), treatment group
and disability

Two-way analysis of variance or Friedman's two- way analysis of variance will be used to assess the association between two categorical (including binary) measures and a continuous outcome depending on normality.

Log linear model will be used to assess the association between three binary outcomes.

Chi-square test/Fischer test will be used to assess the association between two binary outcomes.

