2.1 Study objectives

Primary objective: The primary objective of this trial is to determine whether synovial molecular profiles (=drug target signatures) can inform treatment response to abatacept in early RA..

To this aim, we will compare the change in Clinical Disease Activity Index (CDAI) score at 16 weeks between the biomarker positive and the biomarker negative patients within the abatacept group (i.e. Group 1 vs Group 3) Fig.1 Study Scheme diagram. The primary trial hypothesis is that biomarker positive patients treated according to their highest expressed biomarker will have lower CDAI response at 16 weeks compared to biomarker negative patients.

[figure not shown]
This primary analysis has been chosen as we want to establish a difference in response rates in the treatment in the biomarker arm first, and the trial has been powered for this.

Secondary objectives:

The following analysis will be done:

- Compare patients treated according to their biomarker in the intervention arm against the control arm as a whole (i.e. Group 1 vs 3+4), to determine the enrichment in response in the treatment allocation arm vs the standard of care response rate.
- II. Assess the efficacy of treatment allocation according to biomarker compared to random allocation, we will compare the biomarker positive patients in the intervention arm vs the biomarker positive patients in the control arm (i.e. Group 1 vs Group 4)
- III. Assess the efficacy of the strategy as a whole against the current clinical practice by comparing the control vs intervention arm (i.e. Groups 1 + 2 vs Group 3+4)

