4.7 General considerations

For each treatment group and biomarker, the following will be presented:

- Number and percentage of subjects screened, not randomised/assigned treatment, randomised/assigned treatment, randomised/assigned treatment and not started treatment, discontinued, and completed.
- Number and percentage of subjects randomised at each site.
- Number and percentage of subjects in each analysis set (ITT) overall and by visit.
- Number and percentage of subjects excluded from each analysis set by reason for exclusion.
- Number and percentage of withdrawals (withdraw consent to any further participation in the trial) and treatment cessation, by reason for discontinuation and visit.

5. Interim analysis and timing for analysis

No interim analysis is planned for the current trial. However, the TSC will review the accruing trial data every year during the recruitment phase of the study and assess whether there are any safety issues that should be brought to participants' attention or any reasons for the trial not to continue. TSC reports will consist of an open report where the accrual data will be described without any information on the arm patients have been allocated to, and a closed report where any safety issues by treatment arm will be presented. No stopping rule will be used. See section 9 for further detail. The trial data will be analysed following database lock.

6. Efficacy analysis

The listed measures in Table 2 are to be used in the analyses. The analyses will be carried out in STATA 18 or higher.

In hypothesis testing, the null hypothesis is rejected at (two-sided) significance level 0.05 unless otherwise specified.

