6.1 Main analyses

6.1.1 Primary endpoint

The primary endpoint of the study will be a continuous outcome of CDAI measure at 16 weeks (visit 7).

The primary analysis will assess the difference in the CDAI comparing the difference in response between the abatacept and placebo groups with the biomarker positive group against the difference in response between the abatacept and placebo groups with the biomarker negative group. This analysis will be on an ITT basis according to original randomisation allocation.

The differences between the groups on the primary outcome will be tested with a mixed-effects model with time as a continuous variable. The CDAI is measured at five time points: (1) Baseline, (2) 4 Weeks, (3) 8 Weeks, (4) 12 Weeks, (5) 16 Weeks. The baseline measurement for the primary outcome is the CDAI score after randomisation. This measurement will be included in the analysis as a covariate.

The mixed-effects model results will be presented as P values and 95% CI. In the mixed-effects model we will use both an 'unstructured' and a '1. order autoregressive' covariance matrix and choose the matrix resulting in the lowest Bayesian information criterion. To assess, if the underlying assumptions behind the mixed-effects model analysis are fulfilled, we will investigate normal quantile plots of residuals, standardized residuals, and random effects. If the underlying assumptions behind the mixed-effects model analysis are clearly violated then we will use a generalized estimation equation for the analysis.

The planned primary analysis is a mixed-effects model adjusted for centre and patient comparing the outcome of CDAI between treatment groups in the biomarker arm (Group 1) and non-biomarker arms (Group 3).

A p-value of less than 0.05 will be taken to indicate statistical significance.

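### SAP 6.3, Table 2: the binary exploratory outcomes are modelled separately by biomarker status, so no between-biomarker contrast is planned, and the continuous-outcome entry lists no biomarker term

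*SAP*

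**What the plan says.** SAP 6.3 states the purpose of these analyses: "The robustness of the results on the primary and secondary endpoints will be assessed using the exploratory outcomes as presented in the table below".

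For binary outcomes, Table 2 specifies: "Logistic regression with the treatment, and study as factors will be used". The same entry then adds: "Separate analysis will be performed for biomarker/no biomarker using the ITT population". From the endpoint list in 3.3.3, ACR20/70 response and ACR/EULAR Boolean remission are outcomes of this type.

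For continuous outcomes, Table 2 specifies: "Mixed-effects modelling will be performed with treatment, time and patient as factors, and baseline score as covariate". That entry does not mention separate fits and names no biomarker term.

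The primary result to be checked is worded in two ways. Section 2.1 compares the change in CDAI "between the biomarker positive and the biomarker negative patients within the abatacept group (i.e. Group 1 vs Group 3"); section 2.3 powers that comparison and the end of 6.1.1 repeats it. Earlier in 6.1.1 the primary analysis is described as "comparing the difference in response between the abatacept and placebo groups with the biomarker positive group against the difference in response between the abatacept and". That sentence closes with the corresponding comparison among biomarker-negative patients, so it describes a difference of differences.

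The opening of section 6 sets a general rule that "the null hypothesis is rejected at (two-sided) significance level 0.05 unless otherwise specified". Section 6.7.1 makes subgroup analyses descriptive but does not say whether this covers the stratum models in Table 2.

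**The concern.** A robustness check should address the same contrast as the result it supports. Under either wording, the primary contrast sets biomarker-positive against biomarker-negative patients. Splitting the logistic analysis by biomarker puts the two sides of that contrast into different models, and the plan does not say that they will be brought together again. The continuous entry has the same gap by another route: without a biomarker term, the listed model gives no biomarker contrast.

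What is at stake is the reading of the results. With two stratum-specific p-values and a general 0.05 rule, the natural comparison is significance in one stratum against non-significance in the other. That comparison does not test whether the biomarker informs response to abatacept, and it often looks positive when the treatment effect is the same in both strata.

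A smaller point is the factor *study*. The ITT population in 3.2.1 comes from this one trial, so the term would be constant and adjust for nothing. Centre may be meant, but the text does not say so.

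**Working it through.** **Does any planned model estimate the primary contrast?**

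| Entry | Terms listed | Contrast obtained |
|---|---|---|
| Primary, 2.1 and end of 6.1.1 | Group 1 vs Group 3 | biomarker+ vs biomarker−, within abatacept |
| Primary, earlier in 6.1.1 | difference of differences | treatment × biomarker |
| Table 2, binary | treatment, study; fitted separately by biomarker | treatment effect within each stratum |
| Table 2, continuous | treatment, time, patient, baseline score | treatment effect, no biomarker contrast |

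Neither Table 2 entry names a contrast from the first two rows.

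**Inputs for the size of the problem**

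- Two-sided 0.05 (SAP section 6).
- 45 patients per group and 180 in total (SAP 2.3). Using 45 for each treatment-by-biomarker cell is an assumption: it needs four equal cells, and the SAP gives no biomarker prevalence.
- Response rates are assumed; the SAP gives none.

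**Reproducing the plan's figure.** Table 2 carries no figure, so the check is on the 45. With a difference of 10, SD 14.34 and 90% power:

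n = 2 × 14.34² × (1.960 + 1.282)² / 10² = 43.2, so 44 per group.

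The t-test solution is 44.2, so 45 per group and 90 for the pair, as stated. Allowing for 10% losses, 180/0.90 = 200, also as stated.

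**Equal true effect in both strata, 45 per cell.** Power within one stratum, up to a negligible opposite tail:

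w = Φ(|p₁ − p₀| / SE − 1.96), with SE = √{[p₁(1−p₁) + p₀(1−p₀)]/45}

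The strata are independent, so P(exactly one significant) = 2w(1−w).

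| Abatacept vs placebo | SE | Difference/SE | w | 2w(1−w) |
|---|---|---|---|---|
| 60% vs 40% | 0.1033 | 1.936 | 0.491 | 0.50 |
| 65% vs 35% | 0.1006 | 2.983 | 0.847 | 0.26 |
| 50% vs 35% | 0.1030 | 1.456 | 0.308 | 0.43 |

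With the pooled variance under the null, w becomes 0.475, 0.824 and 0.299, and the last column 0.50, 0.29 and 0.42. By that pooled formula, lower assumed rates give 0.46 (35% vs 20%), 0.50 (40% vs 20%) and 0.40 (45% vs 20%).

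**Simulation.** 2,000 trials, 40% vs 20% in both strata, 45 per cell, logistic fits:

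- exactly one stratum significant: 50.5%;
- exactly one significant and the interaction not significant: 45.3%;
- interaction test rejects: 5.3%.

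Differencing the two separate log odds ratios gave the same z as the joint interaction model (largest discrepancy 6 × 10⁻¹⁴).

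**Precision of the proposed contrasts.** At 60% vs 40% in both strata, each cell contributes 1/(45 × 0.24) = 0.0926 to the variance.

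- Interaction: SE = √(4 × 0.0926) = 0.609, so the 95% CI for the ratio of odds ratios runs a factor exp(1.96 × 0.609) = 3.3 either side of the estimate.
- Biomarker contrast within abatacept: SE = √(2 × 0.0926) = 0.430, a factor of 2.3 either side.

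Interaction power is about 50% if the rates are 50% vs 20% in biomarker-positive and 20% vs 20% in biomarker-negative patients, and about 23% if the latter are 30% vs 20%.

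**The case against.** The strongest reply is that these are exploratory endpoints, so no primary or secondary inference rests on them, and that the SAP never tells anyone to compare p-values across strata. The first part is right and limits the weight of the point. But 6.3 gives these outcomes a supporting role for the primary result, section 6 applies a general 0.05 rule, and nothing labels the stratum models descriptive.

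Several stronger readings are tempting and are not supported:

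- *All of Table 2 is fitted separately by biomarker.* The sentence is attached to the logistic entry only. The table is damaged in the text available, so its full scope cannot be settled from it.
- *The planned analyses cannot check the biomarker contrast.* The two stratum log odds ratios can be differenced, which gives exactly the interaction test. The contrast is recoverable but not planned.
- *There is no adjustment for centre or baseline.* Sections 6.5 and 6.7.2 allow centre adjustment if centres differ significantly, and 8.1 adjusts for imbalanced baseline variables. These rules are conditional, and the Table 2 logistic entry fixes neither adjustment.
- *The continuous model averages the effect over all visits.* This depends on a visit schedule not shown. Section 6.1.1 gives five time points for CDAI; for outcomes measured only at baseline and week 16 there is nothing to average.
- *Only an interaction answers the trial's question.* The SAP powers Group 1 vs Group 3, a contrast within abatacept. The two primary wordings differ and group numbering varies between sections, so the remedy should report both contrasts.

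Finally, 50% is the largest value that 2w(1−w) can take, reached when stratum power is near one half. It should be quoted as the top of a range.

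**Conclusion.** The point holds in limited form. For binary exploratory outcomes the SAP plans stratum-specific treatment effects and no estimate or interval for the between-biomarker contrast whose robustness they are said to assess; for continuous outcomes the listed model has no biomarker term. If the treatment effect were the same in both strata, exactly one would be significant in roughly 26% to 50% of trials, against about 5% for an interaction test. Those figures rest on 45 patients per cell and on assumed response rates, and they do harm only if the stratum p-values are compared. It is an inexpensive improvement to a supporting analysis, not a threat to the trial's main conclusion.

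**What to change.** Revise the Table 2 model entries in 6.3 as follows.

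- Fit one model per exploratory outcome on all ITT patients, with treatment, biomarker and treatment × biomarker.
- For outcomes measured at several visits, add visit as a categorical factor with its interactions, and report the week-16 contrasts.
- Replace *study* with centre and adjust for baseline: the baseline score for continuous outcomes, baseline disease activity for binary ones.
- Report with 95% CIs both the interaction and the biomarker-positive vs biomarker-negative contrast within abatacept, which matches Group 1 vs Group 3.
- Give the stratum-specific treatment effects from the same model, labelled descriptive.

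The cost is SAP wording; no new data are needed. The interaction intervals will be wide, so they should be read as estimates and not as pass-or-fail tests.

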The 3TR PARTNER-RA trial is a double blinded, phase IV, randomised controlled, multi-centre, controlled Clinical Trial of an Investigational Medicinal Product (CTIMP) in a population of patients newly diagnosed with RA (symptoms <12 months) and fulfilling the 2010 ACR/EULAR classification criteria for RA who have an inadequate response to conventional Disease Modifying Anti-Rheumatic Drugs (DMARDs) and are eligible for anti-TNF therapy according to EULAR recommendations: treatment for ≥ 3 months with ≥ 1 csDMARDs¹. Patients recruited to this study will undergo a synovial biopsy at baseline and randomised (1:1) to drug (abatacept) and methotrexate or placebo and methotrexate arm. Patients will be followed up to 16 weeks at which point all patients will be offered a voluntary second synovial biopsy.

In recent years, thanks to the development of minimally invasive ultrasound-guided biopsy² synovial tissue analysis has been proposed as a tool for patient stratification with potential use in clinical practice. In patients with early RA, recent publications indicated that histological³ and molecular⁴ signatures in the synovial tissue are associated with disease outcomes and can stratify response to treatment and predict disease progression, including use of biologics⁵. Recently, the first biopsy-driven Randomised Clinical Trials in RA has shown that the lack of B cell lineage signatures in synovia is associated with lack of response to B cell depleting agent (rituximab) as compared to an alternative medication targeting IL6 receptor (Tocilizumab)⁶.

Patients will be randomised to either an intervention arm or control arm after having a synovial biopsy. If randomised to the intervention arm (treatment by biomarker), the patient's biopsy tissue will be analysed within 2 weeks. In the absence of a target biomarker the patient will be randomised 1:1 to either abatacept or placebo. If the patient is randomised to the control arm, they will be randomised again 1:1 to either Abatacept + MTX or placebo. Patients will continue trial treatment

until 16 weeks, where the treatment response will be assessed as the primary endpoint. There will be a post-treatment visit/call scheduled 30+ days after week 16 (Visit 7). Patients will attend 5 visits (Protocol: Study Schedule, Page 30).

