2.3 Sample size determination

The primary aim of the study is to demonstrate that patients in the "Drug target biomarker" group (Group 1) will have a higher response rate than the "No drug target biomarker" groups (Group 2 and 3)- see section 2.2 for trial diagram.

Using change in CDAI score from baseline (delta CDAI) as the primary outcome, a difference in delta CDAI between the two comparison groups of 10, with a Standard Deviation of 14.34. These are the values that were observed when analysing the difference in delta CDAI between biomarker positive and biomarker negative patients treated with MTX in the PEAC study. Although PEAC patients were not treated with Abatacept, this comparison is expected to be even more in favour of the biomarker positive group using Abatacept together with MTX. Thus, basing the power calculation on the PEAC observed difference is a conservative assumption.

With these assumptions, 90 patients would be needed to detect a significant difference of 10 in delta CDAI with 90% power. Since this would only be for Group 1 and Group 3 (45 patients each), a total of 180 patients would be sufficient for 90% power in the whole trial (Figure 1 Section 2.6). If we assume a 5% dropout rate and also account for an expected 5% of patients that have insufficient RNA for the Nano-string analysis (based on results from the STRAP trial), 200 patients in the whole trial would be sufficient to detect a significant difference (Group 1 vs Group 3) of 10 in delta CDAI with 90% power.

All power calculations were performed using the "twomeans" package in STATA, version SE 18.

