2.4 Randomisation

Randomisation will take place when all the screening procedures and the biopsy visit are completed, and the patient is eligible for enrolment in the study. The randomisation in the study will be applied using simple randomisation, with equal allocation ratio (1:1). All patients with sufficient RNA for analysis will be randomised using simple randomisation (1:1 allocation ratio) into the Control or the Treatment arm according to biomarker arm.

Patients allocated to the control arm of the study, will be subsequently randomised again using simple randomisation with equal treatment allocation ratio (1:1) to Abatacept and Methotrexate therapy or placebo and Methotrexate therapy.

Once the biopsy sample has been received by the central laboratory, patients will be stratified into 2 groups, CD80/CD86 positive (biomarker+) or CD80/CD86 negative (biomarker-) and randomised 1:1 to receive either Abatacept and Methotrexate therapy or placebo and Methotrexate therapy.

3. General Analysis Definitions

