6.1.2 Secondary analyses

The following secondary endpoints will be reported descriptively within each treatment group:

- 1) Percentage of patients with DAS28(ESR)<3.2 (LDA) at 16 weeks
- 2) Percentage of patients with CDAI ≤10 (LDA) at 16 weeks

- 3) Percentage of patients with CDAI remission at 16 weeks
- 4) Change in HAQ-DI at 16 weeks from baseline
- 5) Change in SF-36 at 16 weeks from baseline

Comparisons by groups will be guided by those performed for the primary endpoint in accordance with the following testing outlined above for the primary analysis:

1 vs 3

1 + 2 vs 3+4

All comparisons involving continuous secondary outcomes will be carried using mixed-effects models comparing treatment groups at 16 weeks, adjusted for baseline score, patient and centre. The associated absolute change difference and 95% confidence interval, as well as the mean change in each group will be reported.

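### The mixed model for continuous exploratory outcomes (SAP 6.3, Table 2) leaves out biomarker status, which the plan treats as prognostic and uses in allocating drug: bias on one reading of the allocation, lost precision on the other

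*SAP*

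**What the plan says.** **The model.** Section 6.3, Table 2, continuous outcomes: "Mixed-effects modelling will be performed with treatment, time and patient as factors, and baseline score as covariate". There is no biomarker term and no split by biomarker. The logistic regression entry just before it adds separate analyses with and without the biomarker, and the safety entry reports by treatment and biomarker.

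**Allocation.** The SAP describes it in two ways.
- Section 2 (Introduction), intervention arm: "In the absence of a target biomarker the patient will be randomised 1:1 to either abatacept or placebo". Nothing is said there about randomising biomarker-positive patients in that arm, which is described as treatment by biomarker. The control arm is randomised 1:1 to drug or placebo.
- Section 2.4: "patients will be stratified into 2 groups, CD80/CD86 positive (biomarker+) or CD80/CD86 negative (biomarker-) and randomised 1:1" to abatacept or placebo, each with methotrexate.

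**Prognostic value.** Section 2.3 plans on "a difference in delta CDAI between the two comparison groups of 10, with a Standard Deviation of 14.34". These values were "observed when analysing the difference in delta CDAI between biomarker positive and biomarker negative patients treated with MTX in the PEAC study", that is, without abatacept.

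**Secondary outcomes.** Section 6.1.2 uses "mixed-effects models comparing treatment groups at 16 weeks, adjusted for baseline score, patient and centre" for continuous outcomes, for Group 1 versus 3 and Groups 1+2 versus 3+4. Biomarker is again absent.

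**General rule.** Section 8.1 adjusts for baseline variables imbalanced between treatment groups, whatever the significance test shows. Section 4.4 tabulates the baseline biomarker by treatment.

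**The concern.** A variable that predicts outcome and also governs allocation belongs in the model. If biomarker-positive patients are more likely to receive abatacept, the pooled abatacept group holds more patients who would have improved more on methotrexate anyway, and a drug with no effect would appear to work. If allocation is 1:1 in both biomarker groups, nothing is biased, but variance that the biomarker explains stays in the error term.

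Section 6.3 uses the exploratory outcomes to judge how robust the primary and secondary results are. A model that may favour abatacept because of its case mix is a poor check for that purpose.

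**Working it through.** **Inputs from the SAP.** Gap between biomarker groups 10 CDAI units, SD 14.34, 45 patients in each of Groups 1 and 3, 180 evaluable (section 2.3); two-sided 5% level (opening of section 6); intervention versus control by simple 1:1 randomisation (section 2.4).

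**Assumptions.** Biomarker prevalence 50% (not stated; 45 per group out of 180 suggests it). 14.34 is the SD within a biomarker group. The whole gap survives adjustment for baseline score. *Treatment* in Table 2 means abatacept versus placebo.

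**The plan's own figure.** Section 2.3 says "90 patients would be needed to detect a significant difference of 10 in delta CDAI with 90% power". The normal formula, n = 2(1.960 + 1.282)² × 14.34² / 10², gives 44 per group after rounding up. The t-test solution is 44.2, hence 45 per group and 90 in all, with power 90.5%. The figure is reproduced.

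**Reading A: section 2, all intervention-arm positives receive abatacept (inferred).**
- P(abatacept | positive) = 0.5 × 1 + 0.5 × 0.5 = 0.75; P(abatacept | negative) = 0.50.
- Abatacept: 90 × 0.75 + 90 × 0.50 = 112.5 patients, of whom 67.5/112.5 = 60% are positive.
- Placebo: 90 × 0.25 + 90 × 0.50 = 67.5 patients, of whom 22.5/67.5 = 33.3% are positive.
- Bias with no drug effect = 10 × (0.600 − 0.333) = 2.67 units.
- Variances: 14.34² + 100 × 0.6 × 0.4 = 229.6 on abatacept; 14.34² + 100 × 0.333 × 0.667 = 227.9 on placebo.
- SE = √(229.6/112.5 + 227.9/67.5) = 2.33; bias/SE = 1.146.
- Type I error = Φ(1.146 − 1.96) + Φ(−1.146 − 1.96) = 20.8% + 0.1% = 20.9%.

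A simulation of 10,000 trials gave 20.3% without the biomarker term and 5.0% with it. Sensitivity of the type I error on this reading:

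| Prevalence | Gap | N | Type I error |
|---|---|---|---|
| 50% | 10 | 180 | 20.9% |
| 30% | 10 | 180 | 15.8% |
| 70% | 10 | 180 | 16.9% |
| 50% | 7.5 | 180 | 14.2% |
| 50% | 5 | 180 | 9.2% |
| 50% | 2.5 | 180 | 6.0% |
| 50% | 10 | 200 | 22.7% |

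Taking 14.34 as the SD within each drug group instead gives 22.7% at N = 180.

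**Reading B: section 2.4, 1:1 in each biomarker group.** The biomarker mix is the same on both drugs in expectation, so the bias is 0; simulated type I error was 5.0% with or without the term. At 50% prevalence the biomarker contributes 10² × 0.5 × 0.5 = 25 to the variance. The ratio with and without the term is 14.34²/(14.34² + 25) = 0.892, about 11% less residual variance. The simulated SE falls from 2.27 to 2.15. For an illustrative drug effect of 6 units (assumed) at 90 versus 90, power rises from 75.5% to 80.1%.

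**Groups 1+2 versus 3+4 read as intervention versus control.** Arm is randomised independently of biomarker. Simulated type I error without the term was 4.9% under reading A and 4.8% under reading B. Only precision changes (SE 2.27 against 2.15).

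**The case against.** **The bias rests on an inference.** Section 2 does not say outright that every intervention-arm positive receives abatacept, and section 2.4, the randomisation section, gives 1:1 in both groups. This stands: the bias is conditional. The case for the term is not, because it helps on either reading.

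***Treatment* may not mean pooled drug.** Sections 6.1.1 and 6.1.2 use treatment groups for Group 1 versus 3 and 1+2 versus 3+4, and no pooled drug contrast appears among the listed comparisons. The safety entry, by treatment and biomarker, points to drug but does not settle it. The SAP should define the factor.

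**Section 8.1 could act.** A 60% against 33% split is an imbalance, and section 4.4 would show it. But the rule is applied after the data are seen, has no threshold and does not name the biomarker. Under balanced 1:1 allocation it would not be triggered, and the precision would be lost.

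**Table 2 is damaged in the text at hand.** The sentence on separate biomarker analyses might have covered more than the logistic entry. It comes before the next column label, so the natural reading ties it to that entry.

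**Stronger readings that the SAP does not support.**
- A reader might infer that the 21% also applies to Groups 1+2 versus 3+4. It does not, if that is the arm comparison, because arm is independent of biomarker.
- A reader might carry the 21% over to FACIT, ESS, EQ-5D, ultrasound or histology. The SAP gives no biomarker gap for any of them.
- A reader might add biomarker to every continuous model. Section 2.1 defines Group 1 versus 3 as positive versus negative within abatacept, so the term would remove the contrast. The group labels are also not used consistently: section 2.1 makes 3+4 the control arm, whereas section 2.3 calls Groups 2 and 3 the groups without the target biomarker. If the groups were a cross of biomarker and drug, 1+2 versus 3+4 would itself be the biomarker contrast.

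**Conclusion.** The point holds in conditional form. The continuous exploratory model omits a variable that the SAP itself treats as prognostic and uses in allocating drug.

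On the section 2 reading, a pooled abatacept-versus-placebo contrast on a CDAI outcome is biased by about 2.7 units, with type I error of about 21%. That requires abatacept for all intervention-arm positives, 50% prevalence, 180 patients and the full 10-unit gap after baseline adjustment. It falls to about 16–17% at 30% or 70% prevalence, 14% for a 7.5-unit gap and 9% for a 5-unit gap. On the section 2.4 reading the cost is precision alone, about 11% of residual variance.

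These are exploratory outcomes and the primary analysis is not affected by this point, so the weight is moderate. The change is worth making because these outcomes serve as the robustness check.

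**What to change.** - In Table 2, prespecify biomarker status (positive/negative) as a fixed factor in the continuous mixed models, or analyse by biomarker as the logistic entry does. State whether *treatment* means abatacept versus placebo.
- Reconcile sections 2 and 2.4 on how biomarker-positive patients in the intervention arm are allocated. The term can be added without waiting for this.
- In section 6.1.2, add biomarker to the Groups 1+2 versus 3+4 model only once that contrast is confirmed as intervention versus control arm, as section 2.1 states. Do not add it to Group 1 versus 3.

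The cost is one model term, one degree of freedom and a few lines of text. No new data are needed, since the biomarker is already determined at baseline.
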